Background about migraine and sleep: Most patients believe that many of their migraine attacks are triggered by sleeping too little, sleeping too much, have their sleep interrupted too many times during the night, poor sleep quality, not feeling well-rested in the morning hours after the sleep, etc. These common complaints gave rise to the notion that sleep disturbances are some of the most common triggers of migraine. Moreover, sleep disturbances may be a risk factor for chronification of migraine, the transformation of migraine from episodic to chronic form. If sleep disturbances can trigger migraine attacks or lead to its chronification, it is tempting to propose that drugs that prevent migraine may have an ability to restore normal sleep or attenuate certain aspects of sleep disturbances and by doing so, prevent the initiation of an attack by preventing or modifying its trigger.

Background on fremanezumab and the hypothalamus: Fremanezumab is an anti-CGRP monoclonal antibody and belongs to a class of drugs that effectively prevents migraine. In principle, the size of CGRP (about 150 kD) does not allow it to cross the blood brain barrier (BBB) and enter the brain. It is therefore believed to achieve its preventative effects by acting outside the brain. An exception to this thinking is the hypothalamus, a brain area where the BBB is relatively open and as a result, large molecules may gain some access to its neurons.

B3. DESCRIPTION OF RESEARCH PROTOCOL

A. Study Design – Overview, Methods, Procedures

Overview:

This is a within-person study design that examines treatment effects (changes) using high-resolution assessments. To complete the study, each participant will be observed using daily assessments of **migraine** and **sleep** outcomes before treatment (baseline: 0 to 30 days), and at 1, 2, and 3 months after treatment (injection 1: days 31-60, injection 2: days 61-90, injection 3: days 91-120). In essence, this creates an interrupted time-series design where repeated interventions are introduced at fixed intervals.

Methods:

The study involves 5 visits. The first and last visit will take place at the headache clinic, while the middle three will occur at the Clinical Research Center:

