In clinic visit 1 (day 0), subjects will learn about the study and if they agree to participate, will be consented and screened for eligibility. Those deemed to be eligible will be asked to fill a headache questionnaire and then taught how to fill, at home, a daily e-diary for sleep and a daily e-diary for headache via REDCap. The electronic headache diaries are being collected to allow us to determine how the treatment affects migraine frequency, intensity, and duration. We will also administer a QST procedure prior to starting subjects on study treatment.

In clinic visit 2 (day 30), subjects will visit the CRC to review their e-diaries and receive the first treatment. The treatment is 225 mg (dissolved in 1.5 ml solution) fremanezumab. Fremanezumab (Ajovy) is a monthly dosed anti-CGRP mAb subcutaneous injection. Prior to being started on the study treatment, subjects of child-bearing potential will undergo pregnancy testing.

In clinic visit 3 (day 60), we will review participants' headache and sleep diaries 1 month after receiving the 1st injection and administer the 2nd injection.

In clinic visit 4 (day 90), we will review participants' headache and sleep diaries 1 month after receiving the 2nd injection and administer the 3rd injection.

In clinic visit 5 (day 120), participants will return to the headache clinic to summarize their experience, review their 120-days e-diaries, and provide any feedback they may have about their experience with fremanezumab. We will also do a follow up QST procedure to complete the end of subjects' study participation.

Quantitative Sensory Testing (QST):

QST will be done in a quiet room away from noise and distraction. Patients will be able to choose their most comfortable position (sitting on a chair or laying in bed) during the sensory testing. In each testing session, pain thresholds to hot and mechanical stimulation will be determined in the skin over the site to where the pain is referred to. This site includes most commonly the periorbital and temporal regions. Heat skin stimuli will be delivered through a 30x30 mm² thermode (Q-Sense 2016, Medoc) attached to the skin at a constant pressure and their pain thresholds will be determined by using the *Method of Limit*. The equipment used for quantitative sensory testing has an FDA approval. It imposes no risk or discomfort, and since the patient controls it, stimuli can be stopped at any time.

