Hypothesis 1 – temporal relationship I: Fremanezumab partially prevents migraine by restoring some aspects of sleep disturbances. If this hypothesis is correct, fremanezumab-induced improvement in sleep disturbances will precede the improvement in headache (i.e., the reduction in migraine days per month).

Hypothesis 2 – temporal relationship II: Fremanezumab-induced improvement in sleep disturbances is secondary to the reduction in migraine days per month. If this hypothesis is correct, fremanezumab-induced reduction in migraine or headache days per month will precede the onset of improvement in sleep quality and quantity.

Hypothesis 3 – principle III: The prevention of migraine leads to improved sleep and reduced sleep disorders. If this hypothesis is correct, only fremanezumab responders will experience improved sleep or sleep disturbances whereas fremanezumab non-responders will not experience improvement of sleep disturbances. If this hypothesis is incorrect, sleep quality or quantity will not improve in fremanezumab responders.

Hypothesis 4 – principle IV: Fremanezumab-Improved sleep disturbances lead to reduced migraine or headache days per month. If this hypothesis is correct, only persons with improved sleep disturbances will experience reduction in number of migraine or headache days per month. If this hypothesis is incorrect, patients with improved sleep disturbances may be migraine treatment responders.

[figure not shown]
The primary analyses are designed to estimate the elements of the competing hypotheses (i.e., temporal changes in migraine and sleep). To contrast these hypotheses, we will employ multivariate multilevel regression models as summarized by MacCallum et al.⁷³ and Goldstein.⁷⁴ This approach to modeling within-person change does not have the limitations of a change score approach (i.e., unreliability of residualized change scores), or percentage change approaches (i.e., floor effects, heterogeneous variances) where predictors and outcomes are reduced to differences among measurement occasions. A multivariate modeling approach will allow a direct test of all study hypotheses while maintaining a conservative Type-I error rate. Briefly, parsimonious models will be specified for outcomes and lagged (Y_{t-1}) and synchronous (Y_t) representations of each of the proposed mechanisms modeling time with both linear and quadratic change parameters. This model form will

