capture the expected substantial early-treatment changes in mechanisms (emerging via reductions in daily headache probability and/or increased sleep quality), or more gradual changes that may occur over the full treatment period. The pre-treatment values and change parameters will be specified as individual-level random effects; this effectively allows a unique trajectory to be specified for each individual and for each outcome. These trajectories will then be aggregated using a series of fixed main effects and interactions that directly correspond to each of our specific hypotheses.

In hypothesis 1, lagged sleep trajectories (t-1, t-2, and t-3) are hypothesized to exhibit statistically significant associations with headache probability such that greater increases in sleep are associated with greater reductions in migraine activity. The opposite is assumed in hypothesis 2 where lagged headache trajectories are hypothesized to exhibit statistically significant associations with sleep such that greater reductions in migraine activity are associated with greater increases in sleep. The best fitting model, using lags of either/both will be estimated using nested models and likelihood ratio tests to evaluate the best fitting hypothesis.

Secondary analyses: In addition to testing primary hypotheses, this study will provide a rich source of data to examine effects on other mechanisms. First, analyses will consider questions of “for whom does treatment work?” We will test whether pre-treatment levels of outcomes lead to differential response to treatments (ie, association between intercepts and slopes), which could provide preliminary evidence that, for instance, individuals with worse sleep respond best to treatment. Second, we will estimate the primary models using additional dichotomizations such as ‘responders’ for both sleep and migraine activity (> 50% change). For these analyses, treatment phase (baseline, treatment) and responder (no, yes) will be fixed factors with associations between response groups evaluated using frequency counts and odds ratios (95%CI). In a final set of models, we will use three treatment phases (baseline, early treatment, late treatment) to examine the cross-lagged association of responders and non-responders by treatment phase.

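### The primary models name no injection term; on daily data, linear plus quadratic time misfits an abrupt day-30 shift and can inflate the H1 and H2 lag tests

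*Combined protocol and SAP*

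**What the plan says.** All references are to the combined protocol and SAP.

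- **Design** (B3.A, Overview): "In essence, this creates an interrupted time-series design where repeated interventions are introduced at fixed intervals".
- **Start of treatment** (B3.A, Methods): "In clinic visit 2 (day 30), subjects will visit the CRC to review their e-diaries and receive the first treatment". The Overview counts days 31 to 60 as the first treated month.
- **Primary models** (B3.B, Data Analysis): outcomes and lagged terms are modelled by "modeling time with both linear and quadratic change parameters". This form is said to "capture the expected substantial early-treatment changes in mechanisms" as well as slower change over the whole treatment period. The person-level part is described thus: "The pre-treatment values and change parameters will be specified as individual-level random effects". Further fixed effects and interactions are mentioned but not listed.
- **Decision rule** (same section): hypothesis 1 (H1, sleep leads migraine) and hypothesis 2 (H2, migraine leads sleep) are judged by lags t-1 to t-3, using nested models and likelihood ratio tests.
- **Where phase is named** (B3.B, Secondary analyses): in the responder models, "For these analyses, treatment phase (baseline, treatment) and responder (no, yes) will be fixed factors", and in a final set of three-phase models.
- **Time unit**: Sample Size Justification uses four monthly aggregates. Data Analysis refers to a daily headache probability and three lags. Neither section fixes the unit for the lag models.

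**The concern.** An interrupted time series is normally analysed with a term for the interruption. Here the named time terms form one smooth curve through the untreated and treated days. If the drug changes an outcome quickly after day 30, that curve is too high just before the injection and too low just after it. The leftover error is strongly autocorrelated. If sleep and migraine both shift, they share it.

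Yesterday's sleep can then appear to predict today's migraine, and the reverse, when the drug simply acts on both. The sign of the false association is the one that H1 and H2 predict. Which outcome leads the other is the study's central question, so a trial with no lead in either direction could be reported as support for H1 or H2.

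**Working it through.** The plan gives no figure for model fit or for the error rate of the lag tests, so there is none to reproduce. Its power figure concerns correlated slopes and does not enter here.

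**Step 1. Can a quadratic follow a day-30 step?** Inputs from the plan: 30 untreated days, then 90 treated days. Let y(t) = 0 for t ≤ 30 and 1 for t = 31 to 120. The least-squares fit on 1, t, t² is

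f(t) = −0.298 + 0.03302 t − 0.0001954 t².

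- Day 30: −0.298 + 0.991 − 0.176 = 0.517. The fit is at 52% of the step before any drug effect, so the residual is −0.52; on day 31 it is +0.46.
- Day 1: −0.27. The fit therefore climbs from −0.27 to +0.52 during the untreated month.
- The peak is near 0.03302 / (2 × 0.0001954) ≈ day 84, after which the fit falls to 0.85 on day 120.
- Total sum of squares = 120 × 0.25 × 0.75 = 22.5; residual sum = 4.57; R² = 1 − 4.57/22.5 = 0.80. The lag-1 autocorrelation of the residual is about 0.9.

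With gradual onset, y = 1 − exp(−(t − 30)/τ) after day 30, the largest misfit is 0.42, 0.34 and 0.22 of the final shift for τ = 7, 14 and 30 days.

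**Step 2. Does the misfit reach the lag tests?** Simulations used N = 100, 120 days and no effect of either outcome on the other. Assumptions not in the documents: migraine-day probability about 0.40 falling to about 0.20 in rows B and C, and sleep shifts in daily within-person SD. Row A shifts both outcomes by 0.5 SD. All rows have immediate onset.

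| Check | Shift (SD) | False positives, quadratic only | With phase terms |
|---|---|---|---|
| A. Lag 1, person-level quadratic removed, robust z, 1,000 runs | 0.5 | 18.0% / 15.8% | 5.3% / 5.4% |
| B. Mixed model, 3-df likelihood ratio test, 300 runs (H1 / H2) | 0.3 | 7% / 8% | 5% / 3% |
| B | 0.5 | 13% / 14% | 5% / 4% |
| B | 0.8 | 29% / 34% | 5% / 4% |
| C. Lag 1, binary migraine, 500 runs | 0.5 | 12% / 13% | 5% / 5% |
| C | 0.8 | 27% / 30% | 5% / 8% |
| D. Lag 1, segmented phase terms | 0.5 | 15% to 18% | 5% to 6% |
| D | 0.8 | 28% to 31% | 5% to 6% |

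Row B is closest to the plan's rule. Its Monte Carlo standard error is √(0.05 × 0.95/300) = 1.3 points at 5% and √(0.3 × 0.7/300) = 2.6 points at 30%. It uses a linear probability model, no synchronous term and no autocorrelated errors. A separate check found that adding the planned synchronous term does not remove the inflation.

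**Step 3. When does it fade?** Method B with a 0.8 SD sleep shift (H1 / H2):

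- Onset τ = 7 days: 11% / 15%; 14 days: 6% / 8%; 30 days: 6% / 4%.
- Only one outcome shifts: 4% to 5%.

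**Step 4. Monthly data.** With one lag, the outcome occasions are M1 to M3. Three time parameters fit three means exactly, so no phase misfit is left. With unrelated person-level shifts the rates are 4% to 7% (H1) and 3% to 5% (H2). With three monthly lags only M3 remains as an outcome.

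**The case against.** **The unit may be monthly.** The only place that sets out measurement occasions uses four monthly aggregates, and H1 and H2 are worded in migraine days per month. In a monthly lag-1 model the problem disappears. This stands as a condition. It does not settle the matter, because three lags leave a monthly model one outcome occasion, and a daily headache probability points the other way.

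**The effect needs particular circumstances.** A reader might infer that a quadratic can never follow the treatment effect and that false lag effects in both directions must result. The documents do not support that. The plan itself allows gradual change, and Step 3 shows near-nominal rates for slow onset or a shift in one outcome only. Both tests are falsely positive in the same trial in 0.3% of runs at 0.5 SD, 10% at 0.8 SD and 23% at 1.0 SD.

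**Large shifts are hard to reach for migraine.** At a probability of 0.40 the daily SD is √(0.4 × 0.6) = 0.49, so 0.5 SD is a fall of 0.245, or 61%. At the entry minimum of 8 days in 30 the SD is 0.44, and halving the days is only 0.133/0.44 = 0.30 SD. This weakens row A. Rows B and C rest on a fall from 0.40 to 0.20, with only the sleep shift varied.

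**Counting any significant lag would overstate the problem.** That rule gives 17% to 18% even with phase terms, which is multiplicity. The plan specifies likelihood ratio tests.

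**Phase may be among the unlisted fixed effects.** It may, but the plan does not say so. Phase terms in secondary models do not protect the primary tests.

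**Conclusion.** The point holds conditionally, with medium confidence. The primary models name no phase term, and the assertion that linear plus quadratic time captures substantial early change is not borne out for an abrupt change in daily data.

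Four conditions are needed for material inflation: daily data, a shift in both outcomes, fairly abrupt onset, and a sleep shift of about 0.5 daily SD or more. Under these, the nominal 5% lag tests reject in about 13% to 18% of null trials at 0.5 SD (one cell at 12%) and 27% to 34% at 0.8 SD, against about 4% to 8% with phase terms. Shift sizes and onset are assumptions; the documents give neither.

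A reader might also infer that a diary level shift would serve as the estimate of both primary outcomes. It would not: the sleep primary outcome is the Insomnia Severity Index (B3.A, Primary Outcome Measures), a 0 to 28 questionnaire score that a sleep-diary shift does not estimate.

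**What to change.** In B3.B, Data Analysis:

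1. State that the primary lag models use daily data.
2. Replace the quadratic, for each outcome, with segmented terms: baseline level, baseline slope, level shift after injection 1 with person-level variation, and a post-injection slope or time-since-injection term.
3. Include the lagged phase indicator wherever a lagged predictor enters.
4. Keep the linear plus quadratic model as a sensitivity analysis.

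A curved time-since-injection term is the safer choice in item 2. In method B a bare step left 5% / 10% at τ = 7 days. For that onset, least squares over days 1 to 120 gives R² 0.89 for the quadratic, 0.93 for the straight segmented terms (1, t, step, s, where s is days since injection 1), and 0.997 when log(1 + s) is added. The lag tests were not simulated with this curved term.

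The cost is a few extra parameters. The segmented mean has four time terms per outcome instead of three, plus one person-level shift variance with its covariances, one more term if curved, and the lagged indicators. Each participant contributes about 120 days. No visit or data collection changes.

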This primary outcome measures changes in number of migraine days per month before and during treatment. The number of migraine days per month will be captured using a validated headache questionnaire and scores as follows: 0-8 migraine days per month = low frequency episodic migraine, 9-14 migraine days per month = high frequency episodic migraine, 15-30 migraine days per month = chronic migraine.

[figure not shown]
Assessments of headache and sleep:

At screening (visit 1), headache severity and impact will be assessed based on patients' interviews and HIT-6. Sleep quality will be assessed using the Insomnia Severity Index.

(<https://cbtscience.files.wordpress.com/2014/02/insomniaseverityindex.pdf>).

On days 30, 60, 90 and 120, baseline and treatment impact on headache and sleep will be assessed using the Headache e-diary and the consensus sleep diary [Carney et al., (2012) *The consensus sleep diary: Standardizing prospective sleep self-monitoring*, Sleep Vol.35, No.2, pp.287-302], the latter of which captures total sleep time, sleep latency, wake after sleep onset, number of awakenings, quality, sleep efficiency, and trouble staying awake.

Study flow chart

B. Statistical Considerations

Sample Size Justification:

Although precise sample size calculations are difficult given the novelty of the hypotheses and hierarchical structure of the data, a simulation was created using the “SIMR” package in R and R-Studio. Enrolling $N = 100$ with 4 measurement occasions (baseline, M1, M2, M3) that are created by aggregating the daily measurements from each month provides sufficient power to detect even small associations between changes in sleep and migraine activity. For example, fitting a linear mixed effects model assuming a random intercept, a modest association between intercept and slope ($r = -0.50$), unit variances for the fixed and random effects (i.e., z-scores), and $\alpha = 0.05$, this sample size will provide 95% power (95%CI: 75.1% to 99.9%) to detect correlations between slopes (i.e., changes in migraine and sleep) as small as $r = 0.15$. Differences smaller than this magnitude are unlikely to be clinically meaningful.

Data Analysis:

To fulfill the study’s purpose, 4 hypothesis are being proposed:

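### If the lags are daily, the primary lag models need day-of-week terms: a shared weekly rhythm can mimic sleep leading headache, headache leading sleep, or both

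*Combined protocol and SAP*

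**What the plan says.** Section B3.B, Data Analysis, describes multivariate multilevel models with "lagged (Y_{t-1}) and synchronous (Y_t) representations of each of the proposed mechanisms", "modeling time with both linear and quadratic change parameters". Starting values and change parameters are random at the person level. For Hypothesis 1, "lagged sleep trajectories (t-1, t-2, and t-3) are hypothesized to exhibit statistically significant associations with headache probability"; Hypothesis 2 is the mirror image. Nested models with lags of one or both kinds are then compared by likelihood ratio tests to choose between the hypotheses.

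No weekday, weekend or other calendar term is named anywhere. The lag unit is not given either, and the text points both ways:

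- **Towards days.** Section B3.A, Overview, says "each participant will be observed using daily assessments of" migraine and sleep outcomes. Clinic visit 1 sets up "a daily e-diary for sleep and a daily e-diary for headache via REDCap". Data Analysis speaks of early changes "emerging via reductions in daily headache probability and/or increased sleep quality".
- **Towards months.** The Sample Size Justification works with "4 measurement occasions (baseline, M1, M2, M3) that are created by aggregating the daily measurements from each month", and Hypotheses 1 and 2 are framed in migraine days per month.
- **Towards fitted curves.** What is lagged is called a trajectory, and trajectories are described as built from person-level starting values and change parameters.

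**The concern.** There is no comparator group, so the choice between Hypotheses 1 and 2 rests on the time-series model, and within it on the lag terms. Suppose sleep differs on weekend nights and headache risk also varies over the week for an unrelated reason. Yesterday's sleep then carries information about today's weekday, and through it about today's headache. A lag coefficient can be significant with no link between sleep and migraine and no drug effect. Person-level intercepts, slopes and curvature do not absorb this. At stake is a false statement about temporal order, which is the study's central question.

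**Working it through.** **The plan's own figure.** There is none on this point. The stated power concerns correlations between slopes over four monthly occasions, and does not bear on daily lags.

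**Can the time terms absorb a weekly cycle?** 120 / 7 is about 17 cycles. A quadratic turns at most once, so it cannot.

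**Which lag unit is workable?** With four monthly occasions, a model using t-1, t-2 and t-3 jointly leaves 4 − 3 = 1 row per person, or 100 rows. That is too few for person-level linear and quadratic random effects. With daily data there are 100 × (120 − 3) = 11,700 rows. This favours days but does not settle it.

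**Simulation inputs.** From the documents: N = 100, about 120 diary days, lags 1 to 3, a synchronous term, linear and quadratic time per person, alpha 0.05 (taken as two-sided). Assumed: no true sleep–headache link; daily headache probability about 0.4 (entry requires 8 to 25 headache days per month, about 0.27 to 0.83 per day); a weekly rhythm common to all participants, either a weekend step or a sine wave, with headache 0, 1 or 2 days later than sleep. The test was a 3-df Wald test with person-clustered standard errors after removing each person's trend, using a linear model for daily headache. There were 400 runs per setting. The Monte Carlo standard error at 5% is √(0.05 × 0.95 / 400) = 1.1 points.

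**Scale of the assumed rhythms.** Rhythm size is the SD over the week. For a step on 2 of 7 days with mean 0 and SD 1, weekend days sit at 5/√10 = 1.581 and the others at −2/√10 = −0.632, a gap of 2.21. Multiplying by the SD gives the weekend-versus-weekday differences below.

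| Rhythm (sleep / headache, SD over week) | Weekend gap if a step | False positives, sleep leads | False positives, headache leads |
|---|---|---|---|
| Small: 0.1 SD / 2 points | 0.22 SD / 4.4 points | 5–9% | 6–9% |
| Medium: 0.2 SD / 3 points | 0.44 SD / 6.6 points | 11–27% | 11–27% |
| Large: 0.3 SD / 5 points | 0.66 SD / 11.1 points | 30–93% | 34–91% |

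With no rhythm the same tests gave 7.2% and 3.8%, so the small rhythm shows no clear inflation.

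**With six day-of-week indicators.** The rate was 4–10% across all settings and both directions. The highest cell was 9.8% and the next 8.8%, so the rate is roughly, not exactly, nominal.

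**Cross-check with a simpler model.** This used a random intercept, lags only, no synchronous term and 300 runs. Sleep was +0.5 SD on two nights and the headache odds ratio was 1.3 on two days. At probability 0.40, odds of 0.667 × 1.3 = 0.867 give 0.464, or +6.4 points, close to the medium step. False positives were 11.0% with the same days affected and 27.7% with headache one day later. The main simulation without the synchronous term gave 13.0% and 25.2%.

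**Direction.** With a large sine rhythm, both directions were significant together in 68–87% of runs. With a large weekend step and headache one or two days later, only sleep-leads was significant in about 50% (51.8% and 50.3%), and both in 36.5% and 32.5%.

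**Monthly or trajectory reading.** 30 days is four full weeks plus two days, so a monthly mean keeps only those two days of a unit-SD step: 2 × (−0.632)/30 = −0.04 up to 2 × 1.581/30 = +0.11. Monthly lag-1 false positives were 2–8% at every rhythm size, with no fix. Correlating person-level fitted slopes gave 4–5%.

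**Cost of the terms, no rhythm present (800 runs).** The lag-1 standard error was about 0.0047 with and without them. Power for three true lag effects was 46.1%, 81.9% and 97.5% without the terms, and 46.1%, 82.0% and 97.4% with them.

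**Person-specific weeks.** If each participant's week has its own phase, fixed indicators remove nothing. With the terms in the model, sleep-leads false positives were 10–25% (medium) and 25–89% (large).

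**The case against.** The strongest objection is that the premise is not established. The statistical section's only explicit measurement structure is monthly, four occasions allow exactly three lags, and the lagged object is called a trajectory. Under either the monthly or the fitted-curve reading the problem does not arise. This stands, and is why the point is conditional and why stating the lag unit comes first.

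A reader might infer that the plan's daily models will mistake a weekly rhythm for one series preceding the other. The documents do not support that. They do not say the models are daily, and they say nothing about weekly patterns in sleep or headache. The background remark that patients believe "many of their migraine attacks are triggered by sleeping too little, sleeping too much" concerns the link under study; it is not evidence of a calendar confounder. A small rhythm did no visible harm, and a large one often made both directions significant, which singles out neither hypothesis.

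Nor do the documents show that calendar terms are excluded. The model description presents itself as a brief summary, and the secondary models use treatment phase. The term is unspecified, not ruled out.

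Finally, the simulation approximates the planned likelihood ratio comparison with within-person detrending and a linear probability model, so the rates indicate scale only.

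**Conclusion.** The point holds conditionally. The plan represents time in its primary lag models by linear and quadratic change, names no day-of-week term, and leaves open both the lag unit and what is lagged. If the lags are of raw daily values, a weekly rhythm common to participants and shared by both series can create false lag associations in either or both directions: about 5–9%, 11–27% and 30–93% at a nominal 5% for the small, medium and large rhythms assumed. Those sizes, the rhythm's shape and phase, and the daily headache probability of 0.4 are assumptions; whether such a rhythm exists in this population is unknown. Monthly aggregates and smooth fitted trajectories are not affected.

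It would also go too far to say that the indicators remove the problem outright: they deal only with a rhythm that participants share. This is a free improvement, not a defect that invalidates the plan.

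**What to change.** 1. State in Data Analysis whether t-1 to t-3 are days or months, and whether raw values or fitted trajectories are lagged.
2. For any day-level lag model, include day of week as a fixed factor, six indicators derived from the diary date, in both the headache and the sleep equation, and judge the lag terms conditional on it. Specify this before the data are seen, so that it is not a choice made once the favoured hypothesis is known.

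The cost is a line or two of text and no new data. There are 12 terms in all, six per equation, against about 11,700 person-days (6 / 11,700 = 0.05%). One trade-off should be acknowledged: if a true link acted mainly through weekend sleep, the adjusted test would rely on the variation left within weekdays. Person-specific weekly patterns, such as shift work, would remain; person-level day-of-week effects would be needed for those.

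### The lag terms that decide H1 and H2 have no person-level random slope and no robust standard error, so in a daily model their tests are anti-conservative if lag effects differ between patients

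*Combined protocol and SAP*

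**What the plan says.** All of the model description is in section B3.B, Data Analysis.

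- **Random part.** "The pre-treatment values and change parameters will be specified as individual-level random effects". The preceding text defines change over time as linear and quadratic, so the terms named as random are intercepts and time trends.
- **Part that tests the hypotheses.** "These trajectories will then be aggregated using a series of fixed main effects and interactions", which the plan ties to its specific hypotheses. Hypothesis 1 rests on sleep lagged by one, two and three units predicting headache. Hypothesis 2 rests on the reverse. Nested models compared by likelihood ratio tests choose between them.
- **Error rate.** The plan says that the multivariate approach keeps the type I error rate conservative. It gives no figure and no mechanism for this.
- **Not mentioned.** There is no person-level random effect for a lag term, and no robust or clustered standard error or bootstrap. None of these is ruled out.
- **Unit of the lag.** It is not stated. In the B3.A Overview "each participant will be observed using daily assessments of" migraine and sleep, and the Data Analysis text refers to the chance of headache on a given day. The Sample Size Justification instead uses months: "Enrolling $N = 100$ with 4 measurement occasions (baseline, M1, M2, M3) that are created by aggregating the daily measurements from each month".

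**The concern.** A fixed lag coefficient assumes that yesterday's sleep has the same effect on today's headache in every patient. If the effect varies, the average is estimated from about 100 people, but a model with a fixed lag coefficient sets its standard error as if it came from roughly 100 x 117 = 11,700 person-days. Likelihood ratio tests from that model then reject too often.

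The plan itself gives reason to expect variation: its last secondary analysis looks at cross-lagged associations separately in responders and non-responders. Whether sleep or migraine improves first is the central contrast of the primary analyses. A significant lag term could be read as showing that sleep leads migraine on average, when the average effect is zero and patients merely differ.

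**Working it through.** **Inputs from the documents.** N = 100; about 120 diary days per patient; lags of 1, 2 and 3, so 120 - 3 = 117 usable days; alpha 0.05 (two-sided assumed, as sidedness is not stated).

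**Assumptions.** Mean lag effect zero. Between-person SD of the lag log-odds, per SD of sleep, tau = 0 to 0.3. Complete diaries. p(1-p) = 0.235, that is, a daily headache probability p of about 0.38.

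**The plan's own figures.** There is no type I figure for the lag tests to reproduce, only alpha and the general assurance. The stated power is for a different quantity, "to detect correlations between slopes (i.e., changes in migraine and sleep) as small as $r = 0.15", and does not bear on this point.

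**One lag, daily, by formula.** The variance of one person's estimate that the fixed-lag model recognises is 1/(117 x 0.235) = 1/27.5 = 0.036. The true variance is 0.036 + tau². The ratio is f = 1 + 27.5 tau², and the actual error rate is 2[1 - Φ(1.96/√f)].

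| tau | f | 1.96/√f | Error rate |
|---|---|---|---|
| 0 | 1.00 | 1.96 | 5.0% |
| 0.05 | 1.07 | 1.90 | 5.8% |
| 0.1 | 1.27 | 1.74 | 8.3% |
| 0.2 | 2.10 | 1.35 | 17.6% |
| 0.3 | 3.47 | 1.05 | 29.3% |

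At tau = 0 the nominal 5% is recovered.

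**Daily, by simulation.** Separate logistic simulations of this setting (headache outcome, 100 patients, 117 days) gave the ranges below. The one-lag column also includes the formula.

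| tau | One lag | Three lags jointly |
|---|---|---|
| 0 | about 5% | about 5% |
| 0.1 | 7-8% | 7-14% |
| 0.2 | 14-19% | 23-28% |
| 0.3 | 24-29% | 41-46% |

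Part of the spread is simulation noise: with 300 runs the standard error at 25% is √(0.25 x 0.75/300) = 2.5 points. The three-lag analogue of the formula, P(χ²₃ > 7.815/f), gives 11%, 29% and 52% at tau 0.1, 0.2 and 0.3. That is above the simulated values at 0.3, so the simulated values are used.

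**Effect of the remedy.** Person-clustered standard errors brought the daily rates back to about 3-8%. They stand in here for a random-slope model, which was not itself simulated.

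**Cross-check on a linear scale.** With a continuous outcome, person-specific intercept, linear and quadratic trends removed, and a standardized lag coefficient, the one-lag rate was 4-5% at tau 0, 19-20% at 0.10 and 54-56% at 0.30. These tau values are not comparable with log-odds, but the mechanism is the same.

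**Monthly reading.** Four occasions and a one-month lag leave three rows per person. On the linear scale, f = 1 + 3 tau² gives 5.3%, 6.4% and 8.2% at tau 0.1, 0.2 and 0.3. Simulation gave 5-8% for tau up to 0.3 and 10-13% at 0.5. Three rows are already used up by a person-specific intercept, linear and quadratic term, so a random lag slope could not be estimated. With all three lags in the model, only one row per person remains.

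**The case against.** **The daily unit is not settled.** Hypotheses 1 and 2 are worded in migraine days per month, and the sample size uses months. On that reading inflation is small. This stands, and it is why the size must be given conditionally. Against it, a model with all three lags would keep one row per patient on monthly data, so the daily reading is the more workable one.

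**The hypotheses speak of trajectories.** If what is tested is an association between person-level trajectories, people are already the sampling unit and the argument falls away. The text permits this reading. The lags indexed by time point the other way, and the plan does not resolve it.

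**Silence is not exclusion.** Fixed main effects also exist in a random-slope model, and the plan calls its description brief. This is fair. But the plan lists which terms are random, and the lag terms are not among them.

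**Two stronger readings are tempting.** First, a reader might infer that false H1 or H2 findings will occur at some large rate in this trial. The documents do not support that: they give no between-person SD, with identical lag effects in all patients there is no inflation, and the logistic figures are for the headache outcome only. They also count rejections of either sign, while H1 is directional. By symmetry about half of the one-lag rejections favour H1, for example 24-29% becomes about 12-15%, against a nominal 2.5%. Second, a reader might take the background remark in B2 about "sleeping too little, sleeping too much" as showing that the effect has opposite signs in different patients. It lists complaints that most patients report. One patient may have both, which would be a non-linear effect within a person.

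**The simulated model is simpler than the planned one.** The logistic runs had one outcome and person intercepts. The linear cross-check removed person-specific trends and still showed the inflation, so this does not rescue the tests.

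**Conclusion.** The point holds in conditional form and should be fixed. As written, the random part covers intercepts and time trends, the decisive lag terms are fixed, and nothing in the plan secures the conservative error rate it claims for them. In a daily model whose lag effects vary around zero, the two-sided false-positive rate for the headache outcome rises from about 5% with no variation to 24-29% (one lag) or 41-46% (three lags jointly) at an SD of 0.3.

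These figures rest on assumed SDs, complete diaries and a headache probability of roughly 0.4. With monthly data the rate is about 5-9% for moderate variation. The size for this trial cannot be fixed from the documents; the mechanism, its direction and the remedy can.

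**What to change.** 1. State the unit of t for the lags (day or month).
2. If it is the day, add an uncorrelated person-level random slope for each lag term used to judge H1 and H2, and do the likelihood ratio tests of the average lag effect within that model.
3. Name the fallback if the model does not converge: person-clustered standard errors or a person-level bootstrap.
4. Report the between-person SD of each lag effect beside its average.

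If the unit is the month, steps 2 to 4 do not apply, because random lag slopes cannot be estimated from three rows per person.

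The cost is SAP wording, somewhat longer model fitting and wider confidence intervals. No extra patients, visits or data are needed.
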